### 5.5 Quarterly Visits (Months 3, 6, 9, 12, and 15)

**In addition** to the monthly visit procedures, the following procedures will be performed **each quarter**:

### **Clinical Procedures**

- Perform genital exam.
- Ascertain HIV risk behaviors by standardized interview prior to counseling (must take place prior to risk reduction counseling).
- Administer questionnaire to assess 3-month history of symptomatic STDs, such as genital ulcer disease, vaginal discharge and rectal symptoms
- Provide HIV and STD pre-test and risk reduction counseling
- Assess whether there has been an unexplained weight gain greater than 5 pounds (2.3 kilograms), AND unexplained decreased urine output.
- Collect blood.
- Provide all available test results and post-test counseling.

For participants with anogenital ulcers or other anogenital findings thought to be HSV-related:

 Perform genital exam and collect swab of anogenital ulcers, or other genital findings thought to be HSV-related, for end of study testing.

For female participants:

• Obtain urine for pregnancy test.

### Laboratory Procedures

- HIV serology.
- Storage of left-over sera for CL and on-site specimen archive.
- For unexplained weight gain greater than 5 pounds (2.3 kilograms) AND unexplained decreased urine output, perform serum creatinine testing.

For swabs from participants with genital ulcers or other possible HSV-related genital findings:

• Storage of swabs for end of study testing to determine etiology by PCR at UW.

For female participants:

• Urine pregnancy test.

#### 5.6 Exit Visit (Month 12 or Month 18)

As stated in Section 2.3 above, participants will have scheduled exit visits either at Month 12 or Month 18, dependent upon the duration of their follow-up period.

The exit visit will be identical to the quarterly follow-up visit, however, in addition, syphilis (including titer if RPR is reactive) and treponemal serologies will be performed and sites will provide results by telephone, or in person according to when the result is available, and ensuring that results are communicated to the participant. Participants with positive serology will be referred according to local standard of care. No study medication will be dispensed at this visit.

For participants that are terminating early from the protocol due to HIV seroconversion, the syphilis test should be performed on the second or confirmatory blood draw if available. All other syphilis serology for non-seroconverters will be performed from the first blood draw.

#### 5.7 Interim Visit (ad hoc)

An interim visit includes any visit taking place 5 days before or after a scheduled monthly visit date. The study specific procedures manual will state in detail how these visits will be handled, and the type of forms that should be completed depending on the nature of the visit. All visits will be documented in the participant's study record.

Participants will be instructed to report to the clinic whenever they have a question or a health problem, or if they need additional drug supplies or condoms. Some further reasons for interim visits may include:

- Adverse events;
- Problems with study regimen compliance or possible side effects;
- STD symptoms.

Participants also will be instructed to return to the clinic if they have symptoms of genital herpes between scheduled study visits (i.e., prodromal symptoms or anogenital lesions) for clinical evaluation and additional episodic treatment (acyclovir 400 mg tid for 5 days, as described in the 2002 CDC STD Treatment Guidelines). Genital lesions and other HSV-related anogenital findings will be swabbed and stored at  $-20^{\circ}$  to subsequently assess etiology of these findings by PCR. Symptomatic bacterial STDs will be treated in U.S. sites according to 2002 CDC STD treatment guidelines and according to WHO or local Ministry of Health guidelines in non-US sites (i.e., free syndromic bacterial STD treatment will be offered or referral for free treatment to participants with vaginal and urethral discharge or genital ulcer disease).

### 5.8 Post-Test Visits For Persons Who Test HIV-Positive After Enrollment

Individuals who test HIV-positive after enrollment will be counseled about the interpretation of the test result, and will have another blood test (on a second sample) for repeat HIV antibody testing to confirm the initial HIV positive result. They will be counseled about clinical and social services for persons who are HIV-infected and methods to reduce the likelihood of transmitting HIV to others. They will be scheduled for another visit in approximately two to three weeks to receive the second HIV result and for additional counseling about their HIV infection. If HIV infection is confirmed, they will be referred to any services and other studies for HIV infected persons.

Participants who are confirmed HIV positive during the first HIV test after enrollment will have their enrollment sample tested at the Central Laboratory PCR if possible.

Additionally, participants who become HIV-infected while they are in the study will be offered enrollment into a six-month ancillary study to assess effect of HSV-2 suppression on HIV-1 levels in the first six months after infection ("viral set-point"). This study will have its own protocol and Informed Consent Forms. Participants will cease to have study visits for the HPTN 039 main protocol and no further data will be collected from them for this protocol once their HIV-infection has been confirmed.

# 6 SAFETY MONITORING AND ADVERSE EVENT REPORTING

# 6.1 Safety Monitoring

Close cooperation between the Protocol Chairs, study site investigators, NIAID Medical Officer, CORE Protocol Specialist, HPTN Statistical and Data Management Center (SDMC) Biostatistician and Protocol Operations Coordinator, and other study team members will be necessary in order to monitor participant safety and respond to occurrences of toxicity in a timely manner. The SDMC at SCHARP will prepare routine study progress reports and reports of Serious Adverse Events (SAEs) experienced by study participants (blinded to treatment assignment) for review by the Protocol Team. The team will meet via conference call every two weeks during the initial period of study implementation, and additional ad hoc calls will be convened if required.

This study is subject to oversight and periodic review by an independent Data Safety Monitoring Board (DSMB) (see section 7.7).

# 6.2 Adverse Event Reporting Requirements

Acyclovir has been studied extensively and has a very well -established safety profile with minimal toxicity. Therefore, Adverse Event (AE) collection will be restricted to SAEs only. Information on intercurrent illnesses and AEs not considered serious will not be collected during the course of this study.

Medically significant adverse events for acyclovir are rare. The most severe of these is acute renal failure, which has only been reported in persons with comorbidities and diseases that predispose them to acute renal failure. Additionally, acute renal failure occurred in patients receiving intravenous acyclovir or who had taken a large overdose of oral drug. The main clinical manifestation of acute renal failure in the setting of acyclovir has been seizures. Therefore, renal function will be assessed by serum creatinine in the setting of seizures or symptoms of possible renal insufficiency (i.e., unexplained weight gain and decreased urine output). Seizures and acute renal failure will be documented in the CRF when such an event occurs. Any seizure or other clinical evidence of renal failure will be considered a reportable SAE regardless of severity. Other SAEs that will be reported are those thought to be related to acyclovir administration, with consultation between the site PIs and Protocol Chairs.

Malaria, tuberculosis, bacterial and parasitic causes of gastroenteritis, dengue fever and other viral and parasitic febrile illnesses are endemic diseases prevalent among the populations under study. Therefore, they will not be routinely reported as SAEs during the course of this study. However, any hospitalization of a study participant, for any reason other than childbirth or elective caesereans, will be reported as an SAE.

Any participant who is determined to be HIV positive during follow-up will be terminated from the study. Since use of all study drug will be discontinued at the point of confirmed HIV seroconversion, deaths and SAEs after HIV infection will not be reported.

All deaths, including those resulting from endemic diseases, occurring while participants are on study will be documented in the CRFs and reported as an SAE.

All SAEs as specified above will be collected on appropriate CRFs. Details will be provided in the SSP.

# 7 STATISTICAL CONSIDERATIONS

### 7.1 Review Of Study Design

This is a phase III, multi-site randomized, double-blind, placebo-controlled trial of twice daily acyclovir for prevention of incident HIV infection among HIV-negative, HSV-2 seropositive heterosexual women and MSM at high risk for HIV infection.

Between 2820 and 3012 high-risk, HIV-negative, HSV-2 seropositive heterosexual women and MSM will be enrolled in the study. All efforts will be made to maintain randomized participants in follow-upfor their total follow-up period of 12 to 18 months. During this time, participants will be scheduled for testing ofHIV seroconversion every three months. In addition, participants will return for monthly visits to receive study drug, return bottles with unused study drug from the prior month for a tablet count, and receive counseling about issues related to compliance with the study protocol. Compliance with the study treatment regimen and occurrence of genital lesions and other genital symptoms will be assessed via clinical interview and evaluation of the number of doses remaining in the bottles returned from the previous month's supply of study drug.

# 7.2 Study Endpoints

# 7.2.1 Primary Endpoints

Consistent with the primary study objective, serologically confirmed HIV infection (as determined by the algorithms in appendix II/III or as adjudicated by the Endpoint Review Committee) will be assessed as the primary study endpoint.

# 7.2.2 Secondary Endpoints

Consistent with the secondary study objectives, the following secondary endpoints will be assessed:

- Occurrence and frequency of genital ulcers
- Proportion of doses missed by study participants assigned to twice daily acyclovir and twice daily placebo.

# 7.3 Accrual, Follow-Up, And Sample Size

The overall target sample size for the trial is between 2820 and 3012 (1410 or 1506 in each arm). WSM are anticipated to be enrolled in Zimbabwe, South Africa, and Zambia. MSM will be enrolled in Lima, Iquitos, and Pucallpa, Peru; Seattle, WA, New York City, NY, and San Francisco, CA.

As summarized in the background and rationale sections, previous cohort and nested case control studies of HIV negative, HSV-2 seropositive and seronegative

individuals suggest that HSV-2 increases the risk of acquisition of HIV by a factor of 2.1 to 2.8, as summarized in the Background section. Assuming that therapy will be 80%-90% effective, this study should be designed to detect an overall relative risk of approximately 0.5. This relative risk may vary depending on whether or not the individual is in a stable partnership and the HIV status of partner(s). Women who become pregnant will be discontinued from study medication but will continue to be followed for endpoint information and will be included in their respective randomization group in the primary analysis. The effect of this policy will be to attenuate the expected relative risk towards 1.0 but the effect will be quite small, assuming only about 5% of women become pregnant (and assuming the pregnancies are distributed randomly throughout the follow up period). To accommodate this effect, we have designed the study for an expected RR of 0.51.

Estimates of number of study participants required to meet the objectives of this study depend on the following:

- 1) expected rate of HIV seroconversion in the placebo group;
- 2) the relative reduction of incident HIV infection associated with acyclovir treatment;
- 3) power and size (type I rate) of the study;
- 4) duration of follow-up.

To determine the number of infections (L) that must be observed to achieve a given power  $(1-\beta)$  for a given relative risk (r) and type I error rate ( $\alpha$ ), the following formula is used (Fleming and Harrington, 1991):

$$L = \left\{ \frac{z_{1-\alpha/2} + z_{1-\beta}}{0.5\log(r)} \right\}^2$$

Assuming a two-tailed  $\alpha = 0.05$  and r = 0.51, 93 HIV seroconversions are required to achieve 90% power to detect an overall difference between the acyclovir and placebo groups.

The number of HIV negative individuals per arm (N) that must be followed to achieve a given number of events (L) depends on the duration of follow-up (f), the incidence rate in the baseline group (I), the relative risk (r) and the proportion lost to follow-up (ltf). The relationship between number of persons per arm and number of events is

$$N_{arm} \approx L/[I^*f^*(1+r)^*(1-ltf)]$$

We assume a 3.5% annual incidence rate over the first 12 months of enrollment and a 2.7% annual seroincidence rate in year 2 in WSM and MSM averaged across the participating US and non-US sites.We assume 8% lost to followup in the first year and 2% every 6 months thereafter. The relative risk is 0.51. The target followup is either 12 or 18 months as outlined in section 2.3 above. Newly enrolled participants will be followed for 18 months after enrollment. In addition, the Protocol Team will evaluate the benefit and feasibility of extending follow-up for currently enrolled participants at each site (extending from 12 to 18 months). Following this evaluation, the re-consent process will be further examined in the first month of implementation at each site involved in the process. The protocol team will then determine whether a particular site will continue re-consenting participants at that site, and whether participants who re-consented to additional follow-up will be followed for 12 or 18 months. The sample size for the study will ultimately be determined by the proportion of currently enrolled participants who will be followed for 12 vs 18 months.

Given similar incidence rates and enrollment numbers in the two risk groups (WSM and MSM), similar numbers of HIV seroconversions are expected in each group. With an expected number of 46.5 seroconversions and all other assumptions as above, the power to detect a relative risk of 0.51 in either risk group individually is 0.63 (without any adjustment for multiple testing), whereas the power to detect a relative risk of 0.427 is 0.80.

### 7.4 Random Assignment

Participants who meet the study eligibility criteria will be offered enrollment in the study, and those willing to take part will be assigned at random to either twice daily 400 mg acyclovir suppressive therapy or twice daily placebo. The randomization code will be maintained by the research biostatistician at the HPTN SDMC. Randomization will be stratified by site.

Within each stratum, a variable-size block randomization scheme will be implemented. Randomization numbers will be provided to the sites. Tablets of blinded study drug will be pre-packaged in monthly supplies and labeled with the participant's study drug number.

### 7.5 Blinding

Both participants and study personnel will be blinded to the treatment assignment. Placebo tablets that appear identical to the active drug will be prepared and packaged in a manner that is indistinguishable from the active drug. In spite of these precautions, a limited number of participants in the placebo arm may suspect that they are not receiving active treatment if they continue to have symptomatic herpes lesions. Participants will be counseled that they should not infer their randomization arm on this basis, as HSV recurrences occasionally occur in the setting of daily suppressive therapy. Blinding will remain in place until the study is closed and all data are cleaned and determined to be ready for final analysis. Premature unblinding may be indicated in rare circumstances when a physician decides it is necessary for the provision of medical treatment. Should such a circumstance occur, the investigator should contact the NIAID Medical Officer, Protocol Chair and the SDMC prior to unblinding. Participants who become unblinded by the investigators will continue to be followed for endpoint determinations.

#### 7.6 Data Analysis

### 7.6.1 Primary Analyses

Descriptive analyses will be carried out to determine if the randomization has resulted in treatment and control groups that are similar with respect to key baseline measures. Although treatment will be randomized by site, the distribution of other risk factors, including measures of exposure to HIV (e.g. percent time using condoms, number of partners, sexual practices) will be described by treatment group.

The primary analysis will be a survival analysis using Cox's proportional hazards model with time to detection of HIV infection as the outcome. The analysis will be based on the "intent to treat" principle and the test will be two-sided. The analysis will be stratified by risk group (MSM and heterosexual women) and a pooled relative risk will be calculated. Endpoint information will continue to be collected on women who become pregnant after randomization (although they will be discontinued from treatment during pregnancy) and these women will be included in the analysis in their original randomization group. Any other individuals who choose to discontinue study medication will be asked for permission to continue to collect endpoint information on them. Their results will also be included in the analysis in their original randomization group. Individuals who go on open label suppressive medication ("cross-overs") will be included in the original randomization group. Similarly, individuals who choose to go on open label suppressive medication will be asked to provide endpoint information and will be included in the analysis in their original randomization group. Individuals who drop out of the study and refuse further testing prior to completion of follow-up will be treated as uninformatively censored as of their last valid HIV test.

Interim monitoring for the trial is described in section 7.7.

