Participants who meet the study eligibility criteria will be offered enrollment in the study, and those willing to take part will be randomized to either twice daily oral 400 mg acyclovir or twice daily placebo throughout follow-up. Randomization will be stratified by site. Within each stratum, a variable-size block randomization scheme will be implemented. Female volunteers will also be tested for pregnancy at both screening and enrollment; pregnancy at time of screening or enrollment will be an exclusion criterion. For participants who are found to have one or more bacterial STD(s), every effort should be made to provide free treatment and follow-up care, in accordance with WHO and CDC guidelines, for international and domestic sites, respectively. If abnormal discharge or other clinical evidence of baterial STDs is detected and/or if the wet mount demonstrates T. vaginalis or bacterial vaginosis, participants may be enrolled; however, bacterial STD treatment or a referral for free treatment at a local clinic should be offered during the enrollment visit (unless awaiting RPR/FTA confirmation of active syphilis infection). . All participants, regardless of study arm, will be counseled on the importance of using condoms every time they have intercourse to prevent STD and HIV transmission. Participants will be followed for 12 or 18 months after enrollment. Participants who become HIVinfected (i.e., seroconvert to HIV) at any time during this 12 or18-month period will be offered enrollment into a six month ancillary study. The objective of this ancillary study is to assess the affect of HSV-2 suppression on HIV-1 levels in the first six months after infection ("viral set-point"). This ancillary study will have its own protocol and Informed Consent Forms.

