### 3 STUDY POPULATION

Between 2820 and 3012 high risk HIV-negative, HSV-2 positive WSM and MSM will be selected for the study according to the criteria in Section 3.1, 3.2, and the guidelines in Section 3.4. They will be recruited as described in Section 3.3 and randomized to study drug as described in Section 7.4. Conditions for withdrawal from the study are described in Section 3.6.

The following study sites will participate in this trial, of which three sites will recruit high-risk WSM and four sites will recruit high-risk MSM.

- Harare, Zimbabwe
- Lusaka, Zambia
- Lima, Iquitos, and Pucallpa, Peru
- Seattle, WA, USA
- New York, NY, USA
- San Francisco, CA, USA
- Johannesburg, South Africa

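### Randomisation is blocked within site but the primary Cox model is stratified only by risk group: stratifying by site is a free refinement for HIV and useful protection for the time-to-first-ulcer analysis

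*Supplement*

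**What the plan says.** On allocation, Section 7.4 says "Randomization will be stratified by site", and Section 2.3 adds "Within each stratum, a variable-size block randomization scheme will be implemented". No other stratification factor is named.

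On the primary analysis, Section 7.6.1 says "The primary analysis will be a survival analysis using Cox's proportional hazards model with time to detection of HIV infection as the outcome", that "the test will be two-sided", and that "The analysis will be stratified by risk group (MSM and heterosexual women) and a pooled relative risk will be calculated". Site is neither a stratum nor a covariate in Sections 7.6.1 and 7.6.2, and no reason is given for using risk group instead.

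Section 3 says that "three sites will recruit high-risk WSM and four sites will recruit high-risk MSM", so site determines risk group.

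Section 7.6.2 plans separate Cox models in women and in MSM, a recurrent-event proportional hazards model for genital ulcers, and a time-to-first-recurrence analysis. The two ulcer analyses state no stratification by site or by risk group.

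For sample size, Section 7.3 gives incidence only as a figure "averaged across the participating US and non-US sites". It also lets the 12- or 18-month follow-up mix vary between sites: "The protocol team will then determine whether a particular site will continue re-consenting participants at that site".

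**The concern.** It is usual to analyse by the factors used to randomise. Here the primary model uses a coarser grouping. One MSM stratum puts Peru together with three US cities, and one women's stratum puts Zimbabwe, Zambia and South Africa together. Each stratum therefore assumes a common baseline hazard across its sites.

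When a prognostic factor is left out of a Cox model, the hazard ratio can be pulled toward 1 even if the arms are perfectly balanced on that factor. High-risk participants have their event and leave the risk set sooner, and they leave faster on placebo. The arms still at risk then become less alike. The pull grows with the event proportion and with the spread in site rates. So the question is how large it is for HIV, which is rare, and for genital ulcers, which may not be.

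**Working it through.** **1. The plan's own figures.** Section 7.3 gives two-sided alpha 0.05, power 90% and r = 0.51.

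L = [(1.960 + 1.282) / (0.5 × ln 0.51)]² = 10.507 / 0.33667² = 92.7, rounded up to the stated 93.

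At 18 months with 10% loss, 93 / [(0.035 + 0.5 × 0.027) × 1.51 × 0.90] = 1411 per arm, against the stated 1410. Neither formula contains the strata, so the choice of strata changes neither figure.

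**2. How the strata relate.** Three women's sites and four MSM sites make seven randomisation strata, which collapse into two analysis strata. Site strata contain the risk-group strata. With 93 events there are 93 / 7 ≈ 13 per site on average, enough for a stratified model.

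**3. The mechanism by hand.** Take two equal-sized sites with constant rates and 18 months of follow-up. All site rates here are assumptions, because the documents give none. The pooled rate is the average among those still event-free.

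- HIV, placebo rates 0.01 and 0.08 per year, true ratio 0.51. At 18 months, placebo is (0.01e^−0.015 + 0.08e^−0.12) / (e^−0.015 + e^−0.12) = 0.0808 / 1.872 = 0.0432. Acyclovir is (0.0051e^−0.00765 + 0.0408e^−0.0612) / (e^−0.00765 + e^−0.0612) = 0.0434 / 1.933 = 0.0225. The pooled ratio has moved from 0.51 at the start to 0.52.
- First ulcer, placebo rates 0.2 and 1.6 per year, true ratio 0.50. At 18 months, placebo is (0.2e^−0.3 + 1.6e^−2.4) / (e^−0.3 + e^−2.4) = 0.2933 / 0.8315 = 0.353. Acyclovir is (0.1e^−0.15 + 0.8e^−1.2) / (e^−0.15 + e^−1.2) = 0.3270 / 1.1619 = 0.281. The pooled ratio has moved from 0.50 to 0.80 by the end of follow-up. A Cox estimate averages over this drift.
- Recurrent ulcers, same rates. Participants stay at risk after an ulcer, apart from short treatment periods, so the pooled ratio stays at about (0.1 + 0.8) / (0.2 + 1.6) = 0.50. The attenuation therefore concerns time to first ulcer. The recurrent-event model is little affected under this simple multiplicative effect.

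**4. Simulation, HIV endpoint.** Blocks within seven sites, about 3000 participants, 18 months, 3000 runs per scenario, two-sided 0.05, Cox score (log-rank) test.

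| Assumed site incidence | Type I error, risk-group / site strata | Power at RR 0.51, risk-group / site strata | Mean one-step log RR, risk-group / site strata |
|---|---|---|---|
| Equal | 0.052 / 0.051 | 0.914 / 0.914 | −0.645 / −0.645 |
| 3-fold range | 0.049 / 0.048 | 0.921 / 0.923 | −0.650 / −0.652 |
| 8-fold range | 0.045 / 0.049 | 0.934 / 0.939 | −0.642 / −0.648 |

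The Monte Carlo standard error is about 0.004 to 0.005. The one-step estimates should be compared with each other, not with ln 0.51 = −0.673.

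Two further simulations put two sites on 12 months of follow-up. With incidences of 2 to 5 per 100 person-years, power was 0.9387 against 0.9390 and mean z was −3.447 against −3.451. With site hazards that fell, stayed constant or rose, power was 0.9015 for both and mean z was −3.205 against −3.211.

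**5. Simulation, time to first ulcer.** Seven sites, about 3000 participants, 18 months, true hazard ratio 0.50, 400 runs.

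| Assumed site ulcer rates per year | Mean HR, risk-group strata | Mean HR, site strata |
|---|---|---|
| 0.3 to 0.9 | 0.515 | 0.500 |
| 0.2 to 1.6 | 0.553 | 0.501 |

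In the second row, mean z was −10.8 against −12.6. A separate run gave 0.52 and 0.56 with risk-group strata against about 0.50 with site strata.

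**The case against.** The planned analysis is coherent and fixed in advance. Risk group is the scientific subgroup of the trial: Section 7.3 gives its power and Section 7.6.2 plans a Cox model in each group. Section 7.6.1 itself recalls that treatment is randomised by site, so the authors knew the design. Arms are balanced within every site, so pooling sites does not invalidate the test, and the measured effect on the HIV comparison is within simulation noise. No separate analysis plan is shown, and one could still set strata for the ulcer models or add a site-stratified sensitivity analysis. For the subgroup models, with about 46.5 events each, no simulation shows that site strata cost nothing. All of this stands, and it keeps the point minor.

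A reader might infer that the analysis ignores the randomisation strata. It does not: the risk-group strata are unions of sites and carry the coarse part of the site stratification. A reader might also infer that different follow-up lengths by site undermine the model. They do not: the 12- or 18-month limit is administrative censoring, set without regard to arm, and Cox risk sets handle it. Nor is there a sign that differently shaped site hazards make site strata much better for HIV, since the simulation with mixed shapes found no material gain.

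Nothing in the objection shows a cost to site strata in the primary model. It also leaves the time-to-first-ulcer attenuation unanswered.

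**Conclusion.** This is a minor improvement and not the correction of an error. The mismatch between randomisation strata and analysis strata is in the current text. For HIV its effect is negligible: at most 0.4 percentage points in type I error and 0.5 in power under an assumed eight-fold range in site incidence, with the 93 events and the sample size unchanged.

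The gain is material only for time to first ulcer, and only if ulcers are common and site rates differ. At assumed rates of 0.3 to 0.9 per year a true 0.50 becomes about 0.52. At 0.2 to 1.6 per year it becomes about 0.55 to 0.56, so a 50% reduction is reported as roughly 45%. Those runs used risk-group strata for comparison, whereas the plan states none for these models.

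The conclusion rests on assumed site sizes and site rates, because the documents give only average HIV incidence and no ulcer rates. The recurrent-ulcer model was not in these simulations. The hand calculation suggests little attenuation there, so for that model site strata mainly bring consistency with the design.

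**What to change.** In Section 7.6.1, stratify the primary Cox model by randomisation site, state that this also preserves the risk-group stratification, and keep the risk-group-stratified model as a sensitivity analysis. Define site as the unit used in the randomisation list. Section 3 counts the three Peruvian cities as one site, so the text should say whether the list does too.

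In Section 7.6.2, stratify the time-to-first-ulcer and recurrent-ulcer models by site. The subgroup Cox models may use the same site strata within each risk group.

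If the risk-group strata are kept for the primary model, a one-line justification and a prespecified site-stratified sensitivity analysis would be enough. Either wording should be fixed before unblinding, and the interim comparisons in Section 7.7 should use the same strata as the final test.

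The cost is a sentence or two. No new data are needed, the sample size stays the same, and the simulations show no loss of power for the pooled HIV test.
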